5.6.1.2 Sensitivity Analysis

Sensitivity analyses for the primary safety endpoint will be performed including:

- Analysis using the PP safety analysis population.
- As an additional analysis, analysis will be performed using a logistic regression model fit via generalized estimating equations and a working compound symmetric covariance structure; this allows for the modeling of potential within-subject correlation. The model will consist of only an intercept term; estimates will be transformed to the proportion scale to facilitate comparisons to the primary analysis of the performance goal.
- An additional analysis will be performed based on only the first cycle for each subject. This will be based on an exact binomial method.

For each sensitivity analysis, the estimated endpoint rate and the associated one-sided 95% confidence interval will be calculated.

Statistical Analysis Plan		Page 9 of 11
Sponsor	Study	Version
Senseonics	A Post Approval Study to Evaluate the Long-term Safety and Effectiveness of the Eversense® Continuous Glucose Monitoring (CGM) System	1.0

5.6.2 Primary Effectiveness Endpoint

The primary effectiveness endpoint is Time in range, defined as glucose values between 70 mg/dL and 180 mg/dL, at 12 months compared to the first month post-first sensor insertion.

5.6.2.1 Primary Analysis

Effectiveness will be measured as percentage change in the percent time in range (based on hours) at one month post-first sensor insertion compared to 12 months post-first sensor insertion using a time in range definition of glucose values between 70 mg/dL and 180 mg/dL. The Time in Range will be summarized as the mean of the subject percentages, together with the median, standard deviation, minimum, maximum, and 25th / 75th percentiles.

Summary statistics will also be provided for the change in HbA1c levels from baseline, and average hours of use per day.

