3.6. PRIMARY EFFECTIVENESS ENDPOINT

The primary effectiveness endpoint is Time in Range, which is defined as glucose values between 70 mg/dL and 180 mg/dL, at 12 months post-first Sensor insertion compared to the first month post-first Sensor insertion.

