8.3. OTHER ENDPOINTS

Safety

Other safety endpoints will be summarized using descriptive statistics appropriate to the endpoint being evaluated. There are no formal hypotheses or tests for statistical significance associated with secondary endpoints.

The rates for serious and non-serious adverse events will be summarized as binomial proportions, together with the exact, one-sided upper 95% confidence bound. These will include insertion/removal procedure-related adverse events, and rate of device breakage.

Subgroup analysis of all safety endpoints based on:

- Age (<65 years vs. >65 years, minimum 40 subjects)
- Diabetes type (I vs. II)
- Race (non-Caucasian vs. Caucasian)

Effectiveness

Effectiveness will be measured as percentage change in the percent time in range (based on hours) at one month compared to 12 months using a time in range definition of glucose values between 70 mg/dL and 180 mg/dL. The Time in Range will be summarized as the mean of the subject percentages, together with the median, standard deviation, minimum, maximum, and 25th / 75th percentiles.

Summary statistics will also be provided for the change in HbA1c levels from baseline, and average hours of use per day.

Patient Perspective

Patient satisfaction as measured by validated questionnaires (CGM satisfaction survey and Diabetes Distress Scale) administered at select visits will be reported. The patient questionnaire scores will be summarized as means, median, standard deviation, minimum, maximum, and 25th / 75th percentiles.

Page 39 of 43

Effective Date:#: 20 March

Other Endpoints

Success rates for insertion and removal procedures will be presented to evaluate the

Senseonics, Inc. Confidential Information Protocol #: CTP-0034, Version 10

effectiveness of the training program. Success rate will also be presented based on the HCP experience with insertion and removing Sensors (learning curve by number of cases). It is anticipated that approximately 30% of the insertion and removal procedures will be done by nurse practitioners and physician assistants.

The rates of serious adverse events based on HCP experience with inserting and removing Sensors (learning curve by number of cases) will be examined.

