2.2 Study Endpoints

The primary safety endpoint is incidence of the composite of infection, secondary procedures to remove the Sensor, or procedure-related adverse events of at least moderate severity.

The primary effectiveness endpoint is time in range, defined as glucose values between 70 mg/dL and 180 mg/dL, at 12 months compared to the first month post-first Sensor insertion.

3 Study Design

Prospective, multi-center study at up to 30 sites in the U.S. enrolling up to 400 adult subjects with diabetes (to insert 273 subjects) including at least 40 subjects ≥ 65 years to achieve at least 1400 Sensor cycles. The subjects will have one Sensor inserted by trained health care professionals approximately every 3 to 6 months dependent upon the Sensor used (90-day Eversense Sensor or 180-day Eversense E3 Sensor).

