5.1.1 Descriptive Statistics

Continuous data will be summarized with mean, standard deviation, median, minimum, maximum, and number of evaluable observations. Categorical variables will be summarized with frequency counts and percentages. Confidence intervals may be presented, where appropriate, using the t-distribution for continuous data and Clopper-Pearson Exact method for categorical variables.

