5.3 Handling of Missing Data

All attempts will be made to limit the amount of missing data. Unless otherwise specified, no attempt will be made to impute missing data. If a data point is missing, that data point will not contribute to that portion of the analysis. The number of evaluable observations will be reported in analysis so that extent of missing data can be assessed.

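### SAP 5.6.2.1 and Protocol 8.3 state the primary effectiveness change in the reverse order of the endpoint and give no formula, so it could be reported with the wrong sign

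*SAP*

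**What the plan says.** The endpoint is defined consistently. SAP 2.2 gives time in range "at 12 months compared to the first month post-first Sensor insertion", SAP 5.6.2 repeats it ("at 12 months compared to the first month post-first sensor insertion"), and Protocol 3.6 has "at 12 months post-first Sensor insertion compared to the first month post-first Sensor insertion". The Protocol synopsis agrees. In all of them the first month is the reference.

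The analysis sentences read the other way. SAP 5.6.2.1, directly below the endpoint definition in 5.6.2, measures effectiveness as "percentage change in the percent time in range (based on hours) at one month post-first sensor insertion compared to 12 months". Protocol 8.3 has "Effectiveness will be measured as percentage change in the percent time in range (based on hours) at one month compared to 12 months".

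The summary rule that follows is "The Time in Range will be summarized as the mean of the subject percentages", with median, SD, range and quartiles. Its subject is time in range itself, not the change. For missing data, SAP 5.3 says "If a data point is missing, that data point will not contribute to that portion of the analysis" and adds that numbers evaluable will be reported. Protocol 8.4.2 makes effectiveness descriptive. No formula, denominator or averaging rule for the change appears in either document.

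**The concern.** These two sentences are the only stated analysis of the primary effectiveness endpoint. A percentage change needs a base, and the base they name is month 12. If they are programmed as worded, improvers carry a minus sign and decliners a plus sign.

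The result has more than one use. Protocol 9.6 and SAP 5.10 send interim endpoint summaries to FDA, and Protocol 9.6 says that these are to support decisions by HCPs and patients. SAP 5.7 fits a site model to the primary endpoints, and SAP 5.9 fits subgroup models that include primary effectiveness. In both, p < 0.15 is the threshold for further exploration. Reversing the order changes the denominator as well as the sign, so the estimates and p-values from those models can also depend on which formula is used.

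A second question is size. A percentage change in a quantity that is already a percentage can be computed per subject and averaged, or computed from the two monthly means. These can differ considerably, and the documents do not choose.

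**Working it through.** The documents give no time-in-range values, effect size or SD, so there is no stated figure to reproduce. **All inputs below are assumed.** M1 and M12 are a subject's time in range in the first month and at month 12.

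**1. Sign, one subject.** Endpoint order is 100 × (M12 - M1)/M1. Literal order is 100 × (M1 - M12)/M12.

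| M1 to M12 | Endpoint order | Literal order | Points |
|---|---|---|---|
| 50 to 60 | 10/50 = +20.0% | -10/60 = -16.7% | +10 |
| 60 to 66 | 6/60 = +10.0% | -6/66 = -9.1% | +6 |
| 40 to 60 | 20/40 = +50.0% | -20/60 = -33.3% | +20 |

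The sign reverses for every subject whose value changes.

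**2. Averaging rule.** Take four subjects with M1 = 30, 50, 70, 90 and M12 = 45, 55, 65, 80.
- Mean of subject-level changes: (50.0 + 10.0 - 7.1 - 11.1)/4 = +10.4%.
- Change of the means: (61.25 - 60)/60 = +2.1%.
- Mean difference: +1.25 points.

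**3. Drift of the averaged relative change.** Pairs were simulated with beta margins and a Gaussian copula: month-1 mean 60%, equal SD at both times, within-subject correlation 0.5 to 0.8. With no true change, the mean of subject-level changes is the same in either order, and the median is 0:

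| SD | Correlation 0.8 | Correlation 0.5 |
|---|---|---|
| 10 | +0.6% | +1.6% |
| 15 | +1.7% | +4.2% |
| 20 | +3.9% | +9.9% |

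A low base inflates a ratio more than a high base shrinks it, so the average rises without any shift in time in range.

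**4. A true 2-point fall (60 to 58), correlation 0.8 to 0.5.**
- Endpoint order, mean: -2.8% to -1.8% at SD 10; -1.9% to +0.6% at SD 15; about 0% to about +6% at SD 20.
- Literal order, SD 15: mean +5.5% to +8.2%, median about +3.4%.

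**5. A true improvement, literal order, SD 15, correlation 0.8 to 0.5.**
- 2 points: mean -1.9% to +0.4%, median about -3.1%.
- 5 points: mean -6.8% to -4.6%.

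In these simulations the mean percentage-point difference recovers the true change to within simulation error.

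**6. Different subjects in the two monthly summaries.** Let M1 = 40, 50, 60, 70, 80. The two lowest subjects have no month-12 data and the other three are unchanged. The available-data means are 60 and 70, an apparent (70 - 60)/60 = +16.7%. The three pairs show 0.0%.

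**The case against.** The best defence is that nobody would be misled. Every endpoint definition sets month 12 against the first month, one of them immediately above the disputed sentence, and the phrase can be read loosely as a change from month 1 to month 12. The formula (M1 - M12)/M12 is a literal rendering that appears in neither document. This stands as to intent, and a drafting slip is the likely cause. It does not stand as to the instruction: the same reversal is in both documents, and nothing in either settles the formula.

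Four stronger readings are tempting, and the documents do not support them.
- *A reversed median of the change is already planned.* The listed statistics attach to time in range. If they are shown for each month, a reader can see whether it rose or fell.
- *The change itself may mix different subjects.* A within-subject change needs both values, so under SAP 5.3 a subject without one of them drops out. The mismatch in step 6 concerns separate monthly summaries, or a change computed from their means; numbers evaluable would at least be visible.
- *Even in the right order, a small fall will look like a gain.* That holds only if relative changes are averaged over subjects, and then only for some inputs: never at SD 10, only at the lowest correlation tried at SD 15, and for most of the range at SD 20.
- *Percentage change must be abandoned.* It is a legitimate descriptive measure. Stating the order and base corrects the sign; the change of scale is an option.

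**Conclusion.** The analysis sentences in SAP 5.6.2.1 and Protocol 8.3 contradict the endpoint they are meant to analyse and should be corrected. Followed literally, they reverse the sign for every subject whose time in range changes; that is arithmetic and needs no distributional assumption. At group level the literal mean is not always negative for a small improvement, because the upward drift can offset it.

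The size of the drift, +0.6% to +9.9% under no change, rests wholly on the assumed mean, SD and correlation, and arises only if subject-level relative changes are averaged.

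The consequence is limited to reporting and interpretation. There is no test, margin or power for effectiveness, and the primary safety test is untouched. A reader might infer that the direction of the endpoint is itself undefined; the endpoint definitions do not support that.

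**What to change.** In SAP 5.6.2.1 and Protocol 8.3:
- State the change as month 12 relative to the first month, 100 × (M12 - M1)/M1, computed within subject among subjects with data in both periods.
- Report the number of pairs, the mean and median of the change, and month-1 and month-12 time in range for those same subjects.
- Report the paired difference M12 - M1 in percentage points as well, or use it in place of the relative change. A t-based interval for it is already permitted by SAP 5.1.1 ("Confidence intervals may be presented, where appropriate, using the t-distribution for continuous data").
- Use the same defined variable in the interim reports and in the SAP 5.7 and 5.9 models.

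The cost is about a sentence in each document and minor programming, with no new data. The paired set will be smaller than the month-1 set. If percentage points replace percentage change, interim summaries already submitted would need restating on the new scale; adding the difference alongside avoids that.

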5.6.2.2 Sensitivity Analysis

Sensitivity analyses for the primary safety endpoint will be performed including:

- Analysis using the PP safety analysis population

5.6.3 Additional Safety Endpoints

There are no formal hypotheses or tests for statistical significance associated with additional safety endpoints. Analyses will be based on the general methods outlined in this SAP. The following additional endpoints will be summarized with descriptive statistics, overall, and by subgroups as defined in Section 6.9:

- Rate of all device-related and insertion and removal procedure-related adverse events
- Rate of device breakage
- Rate of device-related and insertion and removal procedure related
- Serious adverse events up to 27 months post-first sensor insertion

5.6.4 Additional Effectiveness Endpoints

There are no formal hypotheses or tests for statistical significance associated with additional effectiveness endpoints. Analyses will be based on the general methods outlined in this SAP. The following additional endpoints will be summarized with descriptive statistics.

- Average hours of use per day
- Change in HbA1c levels at each 6-month interval from baseline

Statistical Analysis Plan		Page 10 of 11
Sponsor	Study	Version
Senseonics	A Post Approval Study to Evaluate the Long-term Safety and Effectiveness of the Eversense® Continuous Glucose Monitoring (CGM) System	1.0

5.6.5 Secondary/Other Endpoints

There are no formal hypotheses or tests for statistical significance associated with secondary endpoints. Analyses will be based on the general methods outlined in this SAP. The following additional endpoints will be summarized with descriptive statistics:

- Patient satisfaction with CGM system use (CGM-SAT scale) including total score and 2 subscale scores (Benefits and Lack of Hassles)
- Patient reported Diabetes Distress Scale (DDS) including the total and 4 subscale scores (Emotional Burden, Physician Distress, Regimen Distress, and Interpersonal Distress)
- Success rate of insertion and removal procedures, overall and by HCP experience (learning curve by number of cases), to evaluate the training program
- Rate of serious adverse events based on HCP experience with the insertion and removal of Sensors (learning curve by number of cases)
- HCP feedback questionnaire regarding insertion/removal
- Residual dexamethasone level in explanted sensors

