3.8. PATIENT PERSPECTIVE ENDPOINT

Patient experiences with the CGM system will be assessed using the CGM Satisfaction Survey which is a validated patient satisfaction questionnaire specifically developed for CGM systems by the Juvenile Diabetes Research Foundation (JDRF) Continuous Glucose Monitoring Study Group. Patients will complete the CGM Satisfaction Survey (a 44-item questionnaire) at 6 months and at 12 and 24 months.

Patients will also complete the Diabetes Distress Scale, which is a 17-item scale that measures four dimensions of distress (emotional burden, regimen distress, interpersonal distress, and physician distress). Patients will complete the Diabetes Distress Scale at baseline, 6, 12 and 24 months.

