5.1.3 Visit Windows

Unless otherwise specified, visit based assessments will be analyzed for each analysis time point according to the nominal visit entered in the Case Report Form (CRF) regardless of if it is out of window.

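### The Diabetes Distress Scale is measured at baseline but no within-subject change is planned, so a difference between visit means could reflect who stayed rather than change in distress

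*SAP*

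**What the plan says.** Protocol 3.8 sets the collection times: "Patients will complete the Diabetes Distress Scale at baseline, 6, 12 and 24 months". Footnote 4 of the visit schedule (Protocol 5.3) makes the DDS the only subject questionnaire at Visit 1, so it is the one patient-reported measure with a value before Sensor use.

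On analysis, Protocol 8.3 states: "The patient questionnaire scores will be summarized as means, median, standard deviation, minimum, maximum, and 25th / 75th percentiles". SAP 5.6.5 lists "Patient reported Diabetes Distress Scale (DDS) including the total and 4 subscale scores" among endpoints to be described, and adds: "There are no formal hypotheses or tests for statistical significance associated with secondary endpoints". The general methods in SAP 5.1.1 name summary statistics but no change measure. SAP 5.1.3 analyses assessments by the nominal visit on the case report form.

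On missing data, SAP 5.3 says: "Unless otherwise specified, no attempt will be made to impute missing data", and "If a data point is missing, that data point will not contribute to that portion of the analysis". It also has the number of evaluable observations reported.

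For HbA1c, SAP 5.6.4 is specific: "Change in HbA1c levels at each 6-month interval from baseline". No section of either document gives the DDS a change from baseline, a paired summary, or a comparison of subjects with and without a later score.

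**The concern.** The usual reason to take a baseline and three follow-up scores is to ask whether distress changed. Read together, the sections give a mean for whoever answered at each visit. Setting the 12- or 24-month mean beside the baseline mean then compares a smaller group with a larger one. Withdrawal is allowed at any time (Protocol 4.3). If subjects with higher distress leave more often, the visit mean falls even though nobody's score has moved; if subjects with lower distress leave more often, it rises. The planned output would not let a reader tell either case from real change. The authors specified change for HbA1c, so its absence for the DDS leaves a programmer with no instruction to produce it. At stake is the interpretation of one descriptive patient-reported endpoint.

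**Working it through.** The documents give no sample size, standard deviation, effect or dropout figure for the DDS, so there is no plan figure to reproduce. The check has a textual part and an illustration.

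**Text, side by side**

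| Item | HbA1c | DDS |
|---|---|---|
| Baseline collected | Yes (Protocol 5.3) | Yes (Protocol 3.8, 5.3) |
| Change from baseline named | Yes (Protocol 8.3; SAP 5.6.2.1, 5.6.4) | No (Protocol 8.3; SAP 5.6.5) |
| Missing values | Available data (SAP 5.3) | Available data (SAP 5.3) |

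**Illustration in scale points.** Both inputs are assumptions:

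- Share lost by the later visit, d: 30% to 57%. The upper value is what 10% loss per 90-day interval gives after eight intervals: 1 − 0.9^8 = 0.5695. That loss rate comes close to the planned cycle total, 273 × (0.9 + … + 0.9^8) = 1,399, but only if every Sensor is a 90-day Sensor and only completed cycles count. The study mixes 90- and 180-day Sensors, so the rate is not a document value.
- Baseline gap between leavers and stayers, Δ: 0.1 to 0.5 points.

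Let stayers have baseline mean S, and let no score change. The baseline mean of everyone is (1 − d)S + d(S + Δ) = S + dΔ. The later mean is S. The apparent change is therefore −dΔ.

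| d | Δ = 0.1 | Δ = 0.3 | Δ = 0.5 |
|---|---|---|---|
| 0.30 | −0.03 | −0.09 | −0.15 |
| 0.5695 | −0.06 | −0.17 | −0.28 |

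In this set-up the paired change in stayers is S − S = 0.

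**Second illustration, in SD units.** Scores are normal and constant. A fraction d leaves, and the tendency to leave has correlation r with the score (assumed 0.2 to 0.4). The apparent change is −r·φ(z)/(1 − d), where z is the normal quantile at 1 − d.

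| d | r = 0.2 | r = 0.4 |
|---|---|---|
| 10% | −0.04 | −0.08 |
| 30% | −0.10 | −0.20 |
| 50% | −0.16 | −0.32 |

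The paired change is again 0. The two scales cannot be converted into each other, because the documents give no DDS standard deviation. Both models agree on direction: the shift grows with the loss and with how strongly leaving is tied to the score.

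**The case against.** **The plan does not exclude a change summary.** Neither document says that only visit-level scores will be shown, and descriptive statistics could include change. This is fair. The point is that the plan does not commit to a change summary, while it does for HbA1c.

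**Missing data will be visible.** SAP 5.3 reports the number evaluable, and SAP 5.4 summarises accountability by visit and early exits by reason. That shows how many are missing and why they left, but not whether they scored differently at baseline.

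**Leaving may be unrelated to distress.** Participation can end once 1,400 cycles are reached (Protocol synopsis and 8.4.3), so some 24-month scores may be missing for administrative reasons. Loss unrelated to the score produces no systematic shift. This stands, and it is why the size is unknown.

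**Paired change is not a cure.** It describes subjects with both scores, and it remains biased if those whose distress worsens leave. Nor is it exactly zero when scores fluctuate. Suppose leaving depends on baseline only, the two scores correlate at 0.6 (assumed), and the stayers' baseline lies at −0.199 SD (the 30%, r = 0.4 case). Their later mean is 0.6 × (−0.199) = −0.119 SD, so the paired change is +0.080 SD. This limit stands, and it is why the fix also shows baseline scores by whether the later score is present.

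**A reader might infer that pairing is clearly more precise.** The documents do not support that. They plan no DDS test, and later responders are also in the baseline mean. With N at baseline and n later, the difference in visit means has variance proportional to 1/N + 1/n − 2ρ/N, against 2(1 − ρ)/n for the paired change. At n = 0.43N and ρ = 0.6 these are 2.13/N and 1.86/N, so the paired standard error is about 6% smaller. At ρ = 0.4 they are 2.53/N and 2.79/N, so it is about 5% larger. Precision is not a reason for the change.

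**Conclusion.** The point holds as a gap in a descriptive analysis. The DDS has a baseline, the plan names only score summaries on available cases, and a difference between visit means could reflect who remained. This requires that leaving is related to the score. The documents give neither a dropout rate nor any relation between distress and dropout, so the 0.03 to 0.28 points are an illustration under assumed loss and assumed baseline gap, not an estimate for this study.

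Two stronger readings are not supported. A reader might infer that the baseline DDS is collected and then left unused; it is one of the scores to be summarised. A reader might also infer that a falling mean would be presented as a patient benefit; the plan contains no DDS hypothesis or claim, and the synopsis does not name the DDS among its endpoints. The primary safety and effectiveness results, the sample size and the study's decisions are unaffected. The point does not extend to the CGM satisfaction survey, which has no baseline. It is minor.

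**What to change.** In SAP 5.6.5 add, for DDS total and each of the four subscales at 6, 12 and 24 months:

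- the mean within-subject change from baseline with a 95% confidence interval, in subjects with both scores;
- the baseline mean of those same subjects;
- baseline DDS by whether the later score is present or absent.

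Keep the visit-level summaries. State that paired change describes those who stayed and does not remove bias if subjects whose distress worsens leave.

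While editing, reconcile the collection times: the schedule table in Protocol 5.3 also marks subject questionnaires at Day 540, whereas Protocol 3.8 lists no 18-month DDS.

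The cost is a short addition to the SAP and one table, with no new data. Setting it out before the analysis also avoids choosing the DDS summary after the results are seen.

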3.4. OTHER SAFETY ENDPOINTS

Other safety endpoints include:

- Rate of all device-related and insertion and removal procedure-related adverse events (serious and non-serious events) up to 27 months post-first Sensor insertion
- Rate of device breakage up to 27 months post-first Sensor insertion
- Rate of device-related and insertion and removal procedure-related serious adverse events up to 27 months post-first Sensor insertion
- Subgroup analysis of safety endpoints based on:
 - Age (<65 years vs. >65 years, minimum 40 subjects)
 - Diabetes type (I vs. II)
- Race (non-Caucasian vs. Caucasian)

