3.9. HCP PERSPECTIVE ENDPOINT

3.10. OTHER ENDPOINTS

Other study endpoints include:

- Success rate of insertion and removal procedures, overall and by HCP experience to evaluate training program.
- Rate of serious adverse events based on HCP experience with the insertion and removal of Sensors (learning curve by number of cases)

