6.1. ADVERSE EVENT DEFINITIONS

Adverse Event (AE) is defined as any untoward medical occurrence, unintended disease or injury, or untoward clinical signs (including abnormal laboratory findings) in subjects, users or other persons, whether or not related to the medical device.

- NOTE 1: This definition includes events related to the medical device or the comparator.
- NOTE 2: This definition includes events related to the procedures involved.

NOTE 3: For users or other persons, this definition is restricted to events related to medical devices.

Serious Adverse Event (SAE) is defined as an adverse event that:

- Leads to death;
- Leads to a serious deterioration in the health of the Subject that either:
 - o Results in life-threatening illness or injury; or
 - o Results in a permanent impairment of a body structure or a body function; or
 - o Requires inpatient or prolonged hospitalization; or
 - Results in medical or surgical intervention to prevent life-threatening illness or injury or permanent impairment to a body structure or a body function.
- Led to fetal distress, fetal death or congenital abnormality or birth defect

NOTE: Planned hospitalization for a pre-existing condition, or a procedure required by the CIP, without serious deterioration in health, is not considered a serious adverse event.

Anticipated adverse events are AEs that have been identified as possible adverse events related to the device or procedure.

Unanticipated adverse device effects (UADEs) are defined as any serious adverse effect on health or safety or any life-threatening problem or death caused by, or associated with, a device, if that effect, problem, or death was not previously identified in nature, severity, or degree of incidence in the study plan or application (including a supplementary plan or application), or any

Protocol #: CTP-0034, Version 10

Confidential Information

Page 29 of 43 Effective Date:#: 20 March

f: CTP-0034, version 10

2023

Senseonics, Inc.

other unanticipated serious problem associated with a device that relates to the rights, safety, or welfare of study subjects.

Severity

Mild: Awareness of a sign or symptom that does not interfere with the Subject's usual activity or is transient, resolves without treatment and with no sequelae

Moderate: Interferes with the Subject's usual activity and/or requires symptomatic treatment

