6.3.1. AE REPORTING PERIOD

Adverse events are reported from enrollment until study participation has ended. Adverse events will be followed until resolution, AE has stabilized, or the study has been completed.

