5.8 Safety Analyses

Adverse events (AE) will be reported for the ITT primary analysis population. AEs will be tabulated with the number of events and subjects with event for each event type and overall. Rates will be reported as the number of subjects who experience at least one event during the analysis interval out of the total number of subjects with follow-up to the beginning of the analysis interval. Serious adverse events will also be tabulated. The rate of all AEs and SAEs reported in the study will be reported.

All AEs and SAEs will also be summarized by relatedness as described above. Adverse events leading to death or study discontinuation will be provided in listing format.

All device deficiencies will be reported in listing format.

Statistical Analysis Plan		Page 11 of 11
Sponsor	Study	Version
Senseonics	A Post Approval Study to Evaluate the Long-term Safety and Effectiveness of the Eversense® Continuous Glucose Monitoring (CGM) System	1.0

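### The only adverse-event outcome planned by HCP case number is all-cause serious adverse events, which dilutes any early-case effect; procedure-related events of any seriousness and the primary composite should be shown too.

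*SAP*

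**What the plan says.** Two outcomes are planned by operator experience.

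- **Procedure success.** Protocol 3.10 lists it as "Success rate of insertion and removal procedures, overall and by HCP experience to evaluate training program". Protocol 8.3 and SAP 5.6.5 add that experience means number of cases. The documents do not define success.
- **Serious adverse events.** Protocol 8.3 says: "The rates of serious adverse events based on HCP experience with inserting and removing Sensors (learning curve by number of cases) will be examined". SAP 5.6.5 has the same endpoint: "Rate of serious adverse events based on HCP experience with the insertion and removal of Sensors (learning curve by number of cases").

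Neither statement of the SAE endpoint restricts it to related events. The definitions behind it are broad. In Protocol 6.1 an adverse event counts "whether or not related to the medical device", and one criterion for a serious event is "Requires inpatient or prolonged hospitalization". On timing, Protocol 6.3.1 says: "Adverse events are reported from enrollment until study participation has ended".

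Elsewhere the plan does restrict. Protocol 3.4 has, as a separate endpoint not split by experience, "Rate of device-related and insertion and removal procedure-related serious adverse events up to 27 months post-first Sensor insertion".

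Three further analyses come close but do not use case number:

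- SAP 5.8: "All AEs and SAEs will also be summarized by relatedness as described above".
- SAP 5.9 compares procedure-related adverse events between providers with and without an MD degree.
- SAP 5.7 presents the primary endpoints by site.

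**The concern.** A learning curve for complications asks whether an operator's first procedures are less safe than later ones. The outcome should therefore be one that the operator can influence. Read as written, a hospital admission for diabetic ketoacidosis or heart disease during the Sensor's wear would be placed on the curve at the operator's case number. Such events occur at roughly the same rate whatever the operator's experience, so they shrink a real difference without creating one.

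Meanwhile many complications that skill plausibly affects, such as a treated site infection, a second procedure to remove the Sensor, or moderate pain or bleeding, need not meet the serious criteria. They fall within the primary composite, but no planned table sets the composite or procedure-related adverse events against case number. A flat SAE curve could then be taken as reassurance about early-case safety from an outcome poorly suited to give it.

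There is also a gap in attribution. A subject on 90-day Sensors has eight insertions and eight removals, possibly by different HCPs. The documents do not say which procedure, or which of inserter and remover, an event belongs to. SAP 5.8 reports adverse-event rates per subject rather than per procedure.

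**Working it through.** **The plan's own figure.** The documents state no rate, event count or precision for the learning curve. The only figure carried over is the expected composite rate of 2.3% (Protocol 8.4.1, SAP 4). It reproduces: 31/1892 = 1.64%, with exact 95% interval 1.12% to 2.32%. That history is per subject, and the plan applies it per cycle; the same is done here.

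**Assumptions, none of them from the documents**

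- 30% of the 1400 cycles are early in an operator's series: 420 early, 980 later. This has no connection with the share of procedures by nurse practitioners and physician assistants in Protocol 8.3.
- Rate of procedure-related SAEs in later cycles: r = 0.1% to 0.5%.
- Rate of unrelated SAEs: b = 0.5% to 4% per cycle, the same early and late. Over 1400 cycles that is 7 to 56 events.
- True early-to-later ratio for related events: 2.0.

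**Dilution.** Apparent ratio = (2r + b)/(r + b).

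| b | r = 0.1% | r = 0.5% |
|---|---|---|
| 0.5% | 0.7/0.6 = 1.17 | 1.5/1.0 = 1.50 |
| 1% | 1.2/1.1 = 1.09 | 2.0/1.5 = 1.33 |
| 2% | 2.2/2.1 = 1.05 | 3.0/2.5 = 1.20 |
| 4% | 4.2/4.1 = 1.02 | 5.0/4.5 = 1.11 |

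**Related SAEs only.** The ratio returns to 2.0, but few events remain: 420 × 0.002 + 980 × 0.001 = 1.8 at the low end, and 420 × 0.010 + 980 × 0.005 = 9.1 at the high end.

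**Primary composite.** With 2.3% in later cycles and 4.6% in early ones: 420 × 0.046 + 980 × 0.023 = 19.3 + 22.5 = 41.9 events.

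**Power, as a yardstick only, since no test is planned.** Two-sided 0.05, normal approximation: power = Φ[(d − 1.96 × se0)/se1], where d is the difference in rates, se0 the pooled and se1 the unpooled standard error.

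- Composite: d = 0.023, se0 = 0.00993, se1 = 0.01129, so Φ(0.313) = 62%.
- Related SAEs only: about 10% (r = 0.1%) to 22% (r = 0.5%).

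The approximation flatters the sparse cases. Fisher's exact test with the same inputs gives about 2% and 15% for related SAEs, and 59% for the composite. The ordering does not change.

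**The case against.** The strongest reply is that the plan already gives much of what is wanted.

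- Training is assessed by the success-rate curve, which is labelled for that purpose; the SAE curve is not. A removal success curve would naturally show failed removals in early cases.
- Every event receives an investigator judgement of relatedness (Protocol 6.1, 6.2). The Clinical Events Committee also adjudicates relatedness (6.2.2), so a related-only curve can be produced from data already collected.
- The endpoint is descriptive and touches neither primary conclusion.

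All of this stands, and it limits the weight of the point. It does not remove it. None of those analyses is by case number except success. Success is undefined, and an insertion that succeeds on the day can later become infected.

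A reader might infer more than the documents support:

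- **That unrelated events dominate the curve, or that it cannot show an early-case problem.** There is no SAE rate and no split by relatedness, so the supported statement is dilution of unknown size.
- **That the composite is free of background events.** Its infection component is not limited to the Sensor site, so some composite events may have nothing to do with the operator.
- **That background exposure could reach 690 person-years** (1400 cycles of 180 days). The stated minimum of 273 inserted subjects, over 27 months, supplies only 273 × 27/12 = 614.

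**Conclusion.** The point holds as an optional improvement. By the text, the SAE-by-experience endpoint is all-cause and covers the whole of participation, and no procedure-specific adverse-event outcome is shown by case number. The direction of the effect, toward no difference, follows if unrelated events are about equally frequent in early and later cases. Its size does not follow from the documents; the 1.02 to 1.50 range rests wholly on the assumed rates and the assumed doubling.

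Restricting the curve to related SAEs cures the dilution but leaves about 2 to 9 events, too few to be informative alone. The useful step is to add outcomes that are not limited to serious events. Even then, about 42 composite events would describe a doubled early risk without settling it.

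**What to change.** In Protocol 3.10 and 8.3 and SAP 5.6.5:

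1. Keep the SAE curve, and also show it for SAEs related to the insertion or removal procedure.
2. Add descriptive tables of procedure-related adverse events of any seriousness, and of the primary composite with each component, by the operator's cumulative case number. Flag infections judged unrelated to the device or procedure.
3. Count insertions and removals separately. Link each event to the HCP who did the relevant procedure, and fix the case-number bands in advance.

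A question on Sensors placed or removed before the study would keep an experienced operator from being counted as a novice. It is optional: the current protocol is dated March 2023 and enrollment was expected to start in early 2019, so the answers would be mostly recall.

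The cost is a few more descriptive tables and a small amount of programming. Relatedness is already assessed, and the planned curve already needs operator case counts. The documents do not state outright that operator identity is captured for every procedure, so that should be confirmed first.
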